Phone: / Fax:	
Status:	Final Protocol (Revised Protocol based on global amendment 2)	
Version and Date:	Version:3.0	Date: 20 Jul 2018
Page 1 of 122		
Proprietary confidential information. © 2018 Boehringer Ingelheim International GmbH or one or more of its affiliated companies. All rights reserved. This document may not - in full or in part - be passed on, reproduced, published or otherwise used without prior written permission.		

Objective(s):	
The primary objective of the study is to evaluate the effect of empagliflozin 10 mg versus placebo on exercise ability using the 6 minute walk test in patients with chronic HF with reduced ejection fraction (LVEF <math>\leq</math> 40%).
 
Secondary objectives are to assess Patient-Reported Outcome (PRO).

Methodology:	Randomised, double blind, placebo controlled, parallel group trial.
Number of patients entered:	300
Number of patients on each treatment:	150 (2 treatment groups)
Diagnosis :	Heart failure (HF) with reduced ejection fraction (EF).
Main in- and exclusion criteria	
Main Inclusion Criteria:
 

• 6MWT distance <math>\leq</math>350 m at screening and at baseline.

• Patients with chronic HF diagnosed for at least 3 months before Visit 1 and currently in NYHA class II-IV

• Chronic HF with reduced EF defined as LVEF <math>\leq</math> 40 % as per echocardiography at Visit 1 per local reading (obtained under stable condition)

• Elevated NT-proBNP > 450 pg/ml for patients without atrial fibrillation (AF) OR > 600 pg/ml for patients with AF as analysed at the Central laboratory at Visit 1

• Patients must be clinically stable and on appropriate and stable dose of medical therapy for HF (such as ACEi, ARB, <math>\beta</math>-blocker, oral diuretics, MRA, ARNI, ivabradine), consistent with prevailing CV guidelines, stable for at least 4 weeks prior to Visit 1(screening) with the exception of diuretics which must have been stable for at least two weeks prior to Visit 1. The investigator must document the reason in case the patient is not on such medication or if not on target dose as per local guidelines.

• Clinically stable at randomization with no signs of heart failure decompensation (as per investigator judgement).

• Appropriate use of medical devices such as cardioverter defibrillator (ICD) or a cardiac resynchronization therapy (CRT) consistent with prevailing local or international CV guidelines, and if a device is required, it must have been implanted for at least 3 months prior to visit 1 for CRT and 1 month prior to visit 1 for ICD.

Main Exclusion Criteria:

- Myocardial infarction (increase in cardiac enzymes in combination with symptoms of ischaemia or newly developed ischaemic ECG changes), coronary artery bypass graft surgery or other major cardiovascular surgery, stroke or TIA in past 90 days prior to Visit 1
- Acute decompensated HF (exacerbation of chronic HF) requiring intravenous (i.v.) diuretics, i.v. inotropes or i.v. vasodilators, or left ventricular assist device within 4 weeks to Visit 1, and during screening period until Visit 2
- Previous or current randomisation in another Empagliflozin Heart Failure trial (i.e. studies 1245.110, 1245.121, 1245-0167)
- Type 1 Diabetes Mellitus (T1DM)
- eGFR < 20 mL/min/1.73 m^2 (CKD-EPIcr) at Visit 1
- Symptomatic hypotension or a SBP < 100 mmHg at Visit 1 or 2
- Systolic blood pressure (SBP) ≥ 180 mmHg at Visit 1 or 2, or SBP >160mmHg at both Visit 1 and 2
- Atrial fibrillation or atrial flutter with a resting heart rate >110 bpm
- Unstable angina pectoris in past 30 days prior to Visit 1
- Largest distance walked in 6 minutes (6MWT) at baseline <100m.
- Any presence of condition that precludes exercise testing such as:
  - claudication,
  - uncontrolled (according to investigator judgement) bradyarrhythmia, or tachyarrhythmia,
  - significant musculoskeletal disease,
  - primary pulmonary hypertension,
  - severe obesity (body mass index ≥40.0 kg/m^2),
  - orthopedic conditions that limit the ability to walk (such as arthritis in the leg, knee or hip injuries)
  - amputation with artificial limb without stable prosthesis function for the past 3 months
  - Any condition that, in the opinion of the investigator, would contraindicate the assessment of 6MWT

	
 
• Patients in a structured (according to Investigator judgement) exercise training program in the 1 month prior to screening or planned to start one during the course of this trial.
 
• Patients with planned implantation of ICD or CRT during the course of the trial.
 
• Treatment with i.v. iron therapy or erythropoietin (EPO) within 3 months prior to screening.
 

Test product(s):	Empagliflozin
dose:	10 mg q.d.
mode of administration:	p.o.
Comparator products:	Placebo
dose:	Not applicable
mode of administration:	p.o.
Duration of treatment:	12 weeks
Endpoints	
Primary Endpoints:
 
 
· Change from baseline to week 12 in exercise capacity as measured by the distance walked in 6 minutes
 
 
Key Secondary Endpoints:
 
 
· Change from baseline to week 12 in Kansas City Cardiomyopathy Questionnaire (KCCQ) Total Symptom Score (TSS)
 
· Change from baseline to week 12 in Chronic Heart Failure Questionnaire Self-Administered Standardized format (CHQ-SAS) dyspnea score
 
 
Other Secondary Endpoints:
 
 
· Change from baseline to week 6 in exercise capacity as measured by the distance walked in 6 minutes
 
· Change from baseline in Clinical Congestion Score at week 12.
 
· Change from baseline in Patient Global Impression of Severity of Heart Failure Symptoms at week 12.
 
· Change from baseline in Patient Global Impression of Dyspnea Severity at week 12.
 
· Patient Global Impression of Change in Heart Failure Symptoms at week 12.
 
· Patient Global Impression of Change in Dyspnea at week 12.
 

	
 
· Change from baseline in N-terminal pro-brain natriuretic peptide (NT-proBNP) at week 12
 

Safety criteria:
	
 
· Adverse events (AE)
 
· Serious adverse events (SAE)
 
· AE of special interest (AESI) (hepatic injury, decreased renal function and ketoacidosis)
 
· Incidence and intensity of AE including serious AE (SAE)
 
· Withdrawal from trial medication due to AE
 
· Clinically relevant new finding or worsening of existing condition on physical examination
 
· Clinically relevant changes in laboratory measurements from baseline
 
· Heart rate and blood pressure in conjunction with exercise testing
 
· ECG findings at scheduled visits reported as AEs
 


Statistical methods:
	
The primary model will be a Wilcoxon rank test on change from baseline to week 12 in 6MWT.
 
The primary model will be conducted on all randomized patients.
 
Both key secondary endpoints will be tested using a Wilcoxon rank test, and both will be tested if the primary endpoint revealed a significant result in favour of empagliflozin. For adjustment of multiplicity of the two key secondary endpoints a Hochberg procedure will be followed.
 
The other secondary endpoints will not be part of the testing hierarchy.
 
Change from baseline to week 6 in exercise capacity as measured by the distance walked in 6 minutes will be evaluated using the same model as for the primary endpoint
 
Change from baseline to week 12 of Clinical Congestion Score will be evaluated using a mixed model repeated measure analysis over time. The model will include the factor treatment and the linear covariate of baseline Clinical Congestion Score.
 
Proportion of patients in every category of global impression of change at week 12 will be evaluated using Cochran-Mantel-Haenszel test.
 
Proportions of patients categorized by the shift in scores between baseline and week 12 in patient global impression of severity score will be evaluated using Cochran-Mantel-Haenszel test.

	The endpoint “Change from baseline in NT-proBNP at week 12” (after log-transformation) will be evaluated using a mixed model repeated measure analysis over time with baseline log-transformed NT-proBNP as a covariate without imputation of missing values.
--	---

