### 3.3.2 Inclusion criteria

1. Of full age of consent (according to local legislation, usually  $\geq 18$  years) at screening.
2. Male or female patients. Women of childbearing potential (WOCBP) must be ready and able to use highly effective methods of birth control per ICH M3 (R2) that result in a low failure rate of less than 1% per year when used consistently and correctly. A list of contraception methods meeting these criteria is provided in the patient information. For sites in Portugal please refer to the contraception methods described in [appendix 10.7](#).
3. Signed and dated written informed consent in accordance with ICH-GCP and local legislation prior to admission to the trial
4. 6MWT distance  $\leq 350$  m at screening and at baseline.

---

 A woman is considered of childbearing potential (WOCBP), i.e. fertile, following menarche and until becoming post-menopausal unless permanently sterile.

A postmenopausal state is defined as no menses for 12 months without an alternative medical cause.

Permanent sterilisation methods include hysterectomy, bilateral salpingectomy and bilateral oophorectomy.

Please note that tubal ligation is NOT accepted as a method of permanent sterilisation and therefore a woman who underwent tubal ligation is still considered as WOCBP. However tubal ligation is considered as a method of highly effective birth control.

5. Patients with chronic HF diagnosed for at least 3 months before Visit 1 and currently in NYHA class II-IV
6. Chronic HF with reduced EF defined as LVEF  $\leq 40\%$  as per echocardiography at Visit 1 as per local reading (obtained under stable condition).
7. Elevated NT-proBNP  $> 450$  pg/ml for patients without atrial fibrillation (AF) OR NT-proBNP  $> 600$  pg/ml for patients with AF as analysed at the Central laboratory at Visit 1
8. Patients must be clinically stable and on appropriate and stable dose of medical therapy for HF (such as ACEi, ARB,  $\beta$ -blocker, oral diuretics, MRA, ARNI, ivabradine), consistent with prevailing CV guidelines, stable for at least 4 weeks prior to Visit 1 (screening) with the exception of diuretics which must have been stable for at least two weeks prior to Visit 1. The investigator must document the reason in case the patient is not on such medication or if not on target dose of any heart failure medication as per local guidelines.

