9. Clinically stable at randomization with no signs of heart failure decompensation (as per investigator judgement).
10. Appropriate use of medical devices such as cardioverter defibrillator (ICD) or a cardiac resynchronization therapy (CRT) consistent with prevailing local or international CV guidelines, and if a device is required, it must have been implanted for at least 3 months prior to visit 1 for CRT and 1 month prior to visit 1 for ICD.

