### 3.3.3 Exclusion criteria

1. Myocardial infarction (increase in cardiac enzymes in combination with symptoms of ischaemia or newly developed ischaemic ECG changes), coronary artery bypass graft surgery or other major cardiovascular surgery, stroke or TIA in past 90 days prior to Visit 1
2. Acute decompensated HF (exacerbation of chronic HF) requiring intravenous (i.v.) diuretics, i.v. inotropes or i.v. vasodilators, or left ventricular assist device within 4 weeks prior to Visit 1, and/or during screening period until Visit 2
3. Previous or current randomisation in another Empagliflozin Heart Failure trial (i.e. studies 1245.110, 1245.121, 1245-0167)
4. Type 1 Diabetes Mellitus (T1DM)
5. Impaired renal function, defined as eGFR  $< 20$  mL/min/1.73 m^2 (CKD-EPIcr) or requiring dialysis, as determined at Visit 1
6. Symptomatic hypotension or a SBP  $< 100$  mmHg at Visit 1 or 2
7. Systolic blood pressure (SBP)  $\geq 180$  mmHg at Visit 1 or 2, or SBP  $> 160$  mmHg at both Visit 1 and 2
8. Atrial fibrillation or atrial flutter with a resting heart rate  $> 110$  bpm documented by ECG at Visit 1 (Screening)
9. Unstable angina pectoris in past 30 days prior to Visit 1
10. Largest distance walked in 6 minutes (6MWT) at baseline  $< 100$  m.
11. Any presence of condition that precludes exercise testing such as:
  - claudication,
  - uncontrolled (according to investigator judgement) bradyarrhythmia or tachyarrhythmia,
  - significant musculoskeletal disease,

- primary pulmonary hypertension,
  - severe obesity (body mass index  $\geq 40.0$  kg/m^2),
  - orthopedic conditions that limit the ability to walk (such as arthritis in the leg, knee or hip injuries)
  - amputation with artificial limb without stable prosthesis function for the past 3 months
  - Any condition that, in the opinion of the investigator, would contraindicate the assessment of 6MWT
12. Patients in a structured (according to Investigator judgement) exercise training program in the 1 month prior to screening or planned to start one during the course of this trial.
  13. Heart transplant recipient, or listed for heart transplant
  14. Currently implanted left ventricular assist device (LVAD)

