29. Current use or prior use of a SGLT-2 inhibitor or combined SGLT-1 and 2 inhibitor within 12 weeks prior to Visit 1 or during screening period until Visit 2 (Randomisation). Discontinuation of a SGLT-2 inhibitor or combined SGLT-1 and 2 inhibitor for the purposes of study enrolment is not permitted.
30. Treatment with i.v. iron therapy or erythropoietin within 3 months prior to screening
31. Currently enrolled in another investigational device or drug study, or less than 30 days since ending another investigational device or drug study(s), or receiving other investigational treatment(s). Patients participating in a purely observational trial will not be excluded
32. Known allergy or hypersensitivity to empagliflozin or other SGLT-2 inhibitors
33. Chronic alcohol or drug abuse or any condition that, in the investigator's opinion, makes them an unreliable trial subject or unlikely to complete the trial
34. Women who are pregnant, nursing, or who plan to become pregnant while in the trial
35. Any other clinical condition that would jeopardise patients safety while participating in this trial, or may prevent the subject from adhering to the trial protocol.

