## 5. ASSESSMENTS

### 5.1 ASSESSMENT OF EFFICACY

#### 5.1.1 Six Minute Walk Test

At all sites, patients will perform an exercise capacity assessment using the 6 minute walk test (6MWT). One 6MWT will be performed at the screening visit, visit 3 and the early discontinuation visit (if applicable). At visits 2 and 4, two 6MWTs will be performed at least 1 hour apart for increasing reliability of the test as well as for decreasing variability. The distances from both tests will be recorded in the eCRF and the largest distance measured will be used for analysis. Testing of the 6MWT at each clinic visit should be preferably performed about the same time of day to minimize intraday variability.

The 6MWTs at Visit 1 and 2 will be performed to assess patient eligibility and as well the screening test will serve as the training test to familiarize patients with the procedure. If the distance walked during any of these 6MWTs is > 350m the patient will be considered a screen failure. If the largest distance walked at Visit 2 is < 100m, the patient will be considered a screen failure. The 6MWT of largest distance performed at Visit 2, will be the baseline result.

Prior to and at the end of the 6MWT, patients will be asked to rate their breathing discomfort and overall fatigue using the Borg Scale.

The 6MWT methodology is described in detail in the ISF and [Appendix 10.1](#). Please refer to [section 6.2.2](#) for preferred order of completion of assessments.

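### For MI, cardiovascular surgery, stroke, TIA and unstable angina, no explicit exclusion window covers the screening period of up to 21 days, so only judgement-based criteria apply there

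*Protocol*

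**What the plan says.** The Protocol flow chart places Visit 1 on days -21 to -4 and Visit 2 on day 1, and section 3.1 gives a screening period of up to three weeks. The baseline walk tests, randomisation and first dose all take place at Visit 2. On the walk tests, section 5.1.1 says: "The 6MWT of largest distance performed at Visit 2, will be the baseline result".

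In section 3.3.3 and the synopsis, several look-back windows end at Visit 1:

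- Exclusion 1 covers myocardial infarction, then "coronary artery bypass graft surgery or other major cardiovascular surgery, stroke or TIA in past 90 days prior to Visit 1".
- Exclusion 9 reads: "Unstable angina pectoris in past 30 days prior to Visit 1".
- Exclusion 17 (untreated ventricular arrhythmia with syncope, no ICD; 3.3.3 only) looks back three months from Visit 1.
- Exclusion 25 (major surgery; 3.3.3 only) looks back 90 days from Visit 1. A second clause bars elective major surgery scheduled during the trial.

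Inclusion 8 (3.3.2 and synopsis) requires HF therapy to be "stable for at least 4 weeks prior to Visit 1 (screening) with the exception of diuretics", which need two weeks. Section 4.2.2.1 repeats both periods with the same anchor.

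Two other exclusions in 3.3.3 carry on past Visit 1. Exclusion 2 (decompensated HF) applies "within 4 weeks prior to Visit 1, and/or during screening period until Visit 2". Exclusion 29 (SGLT-2 inhibitors) applies "within 12 weeks prior to Visit 1 or during screening period until Visit 2 (Randomisation".

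Inclusion 9 applies at Visit 2: "Clinically stable at randomization with no signs of heart failure decompensation (as per investigator judgement". Exclusion 11 (conditions that preclude exercise testing) and exclusion 35 (other conditions that jeopardise safety) are not tied to Visit 1.

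**The concern.** The protocol treats a recent infarction, stroke or TIA as disqualifying for 90 days and unstable angina for 30 days, but it measures those periods back from Visit 1 and leaves the interval up to Visit 2 open. The flow chart re-checks eligibility at Visit 2, but that check re-applies windows that closed at Visit 1. Under the criterion written for the event, an older event excludes the patient and a more recent one does not.

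What is at stake is patient safety: two walk tests and the first dose could follow within days of such an event if the investigator judges the patient stable. It also affects deviation reporting. SAP Table 6.2: 1, code A3.44, flags failures of exclusions 1, 9, 17 and 25 and of inclusion 9. A screening event in a patient judged stable breaches none of these as worded, so this code would not flag it.

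**Working it through.** **1. The gap.** With no day 0, day -21 to day 1 is 21 days, which agrees with the three weeks in section 3.1. Day -4 to day 1 is 4 days. Counting a day 0 gives 22 and 5.

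**2. The criteria side by side.**

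| Criterion | Subject | Window ends | Screening covered by an explicit rule? |
|---|---|---|---|
| Exclusion 2 | Decompensated HF | Visit 2 | Yes |
| Exclusion 29 | SGLT-2 inhibitor use | Visit 2 | Yes |
| Exclusions 6, 7 | Blood pressure | Assessed at Visits 1 and 2 | Yes, at both visits |
| Exclusion 1 | MI, cardiovascular surgery, stroke, TIA | Visit 1 | No |
| Exclusion 9 | Unstable angina | Visit 1 | No |
| Exclusion 17 | Ventricular arrhythmia with syncope | Visit 1 | No; exclusion 11 names uncontrolled arrhythmia, by judgement |
| Exclusion 25 | Major surgery | Visit 1, plus scheduled elective surgery during the trial | Only unscheduled surgery is uncovered |
| Inclusion 8 | Stable HF therapy | Visit 1 | No |

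**3. The ordering.** Take two patients with Visit 1 on day -21. Patient A had an infarction 80 days before Visit 1, which is 80 + 21 = 101 days before randomisation; exclusion 1 applies. Patient B has one 7 days before randomisation, which is 21 - 7 = 14 days after Visit 1; exclusion 1 does not apply. Only inclusion 9, exclusion 11 or exclusion 35 can stop patient B, and each depends on the investigator's assessment.

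**4. How many patients.** The documents give neither the mean gap nor an event rate, so both are assumptions: the midpoint gap, (21 + 4)/2 = 12.5 days, and 5 to 10 such vascular events per 100 patient-years.

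- Uncovered time: 300 x 12.5/365.25 = 10.3 patient-years.
- Events: 10.3 x 0.05 = 0.5 to 10.3 x 0.10 = 1.0.
- If every gap were 4 days: 300 x 4/365.25 = 3.3 patient-years, or 0.2 to 0.3 events.
- If every gap were 21 days: 300 x 21/365.25 = 17.2 patient-years, or 0.9 to 1.7 events.

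These are events during screening. Admitted patients would be fewer, because the judgement-based criteria would stop some or most of them.

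**5. Precision, for inclusion 8.** The plan's SD for change in walking distance is 72 m (section 7.7). Assume that HF therapy changes during screening in a fraction f of patients and adds a shift of SD s to their later change. The added variance relative to plan is f x s^2/72^2:

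- f = 5%, s = 30 m: 0.05 x 900/5184 = 0.9%.
- f = 10%, s = 40 m: 0.10 x 1600/5184 = 3.1%.

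For the larger figure, planned power of 90% corresponds to 1.960 + 1.282 = 3.242 standard errors. Dividing by sqrt(1.031) gives 3.193, and 3.193 - 1.960 = 1.233, which is power of about 89%.

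**The case against.** The strongest reply is that the protocol already guards this interval. Inclusion 9 requires clinical stability in general as well as freedom from decompensation, and it applies at randomisation. Section 3.3 repeats that requirement for study entry and allows re-screening only after at least four weeks of stability. Exclusions 11 and 35 have no Visit 1 limit. Section 8.3.1 requires documented eligibility before allocation. A-code A3.44 in the SAP groups inclusion 9 with exclusions 1, 9, 17 and 25 as one class of unstable conditions.

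Most of this stands. A reader might infer that anyone with such an event in screening satisfies all eligibility criteria as written. The documents do not support that: a patient left unstable by an infarction or stroke would fail inclusion 9. Nor is all major surgery uncovered, given the second clause of exclusion 25. What the reply does not reach is a recent or resolved event, such as a TIA, in a patient judged stable. For decompensated HF, the protocol did not rely on inclusion 9 alone; exclusion 2 adds an explicit window to Visit 2. It gives no reason for treating the vascular events differently.

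A reader might also infer a material loss of precision from therapy changes between the visits. That does not hold either. Section 6.2.2 allows HF background therapy to be adjusted at any time during treatment, so a change the day after baseline is permitted and the design already accepts this noise. Events before randomisation are also balanced between arms in expectation, so no bias arises.

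**Conclusion.** The point holds as a gap in explicit windows. For exclusions 1, 9 and 17, and for unscheduled major surgery under exclusion 25, nothing but judgement-based criteria covers the 4 to 21 days between Visit 1 and Visit 2, whereas exclusions 2 and 29 cover them explicitly. The result is a stated rule that excludes an older event and can let a more recent one through.

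It is a cheap improvement on patient-safety grounds. At the midpoint gap it is expected to affect at most about one of 300 patients. That rests on assumed event rates and, at its upper end, on the judgement-based criteria stopping nobody; section 6.2.1 asks for Visit 2 as soon as eligibility is confirmed, which favours shorter gaps. No sample size or type I error figure changes, and even the least favourable precision assumption above costs about one percentage point of power.

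**What to change.** Reconcile the end of these windows with exclusions 2 and 29, chiefly in exclusions 1 and 9, in both section 3.3.3 and the synopsis. The protocol already has the wording: the clause in exclusions 2 and 29 that extends the window through screening to Visit 2. Exclusion 17 and the look-back in exclusion 25 can take the same clause. If the sponsor intends judgement alone to govern screening for these events, the protocol should say so.

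If the stability window of inclusion 8 is aligned as well, section 4.2.2.1 must change with it, or a new inconsistency results; the precision gain there is negligible.

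The cost is a phrase in a few criteria and a few extra screen failures or re-screens. Re-screening is already allowed case by case under section 3.3, once per patient.
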